This randomized, controlled, double-blind clinical trial was approved by the Ethics Committee of Izmir Katip Celebi University (Approval No: 14/100). Informed consent was obtained from parents, and the study adhered to CONSORT guidelines. A total of 200 healthy children (ASA I), aged 6–12 years, each with two fully erupted permanent mandibular first molars (400 teeth), were enrolled. Using a split-mouth design, one molar received a high-fluoride glass ionomer-based sealant (Fuji Triage, GC Corp., Tokyo, Japan; control), while the contralateral molar was treated with either a CPP-ACP-containing sealant (Fuji VII EP, GC Corp.) or a nano-fluorohydroxyapatite-based sealant (GCP Glass Seal, GCP Dental, The Netherlands). Sample size was calculated using G*Power 3.1.9.7, assuming an effect size of 0.40, $\alpha = 0.05$, and power = 0.80, yielding a minimum of 88 teeth per group. Considering a 15–20% potential loss, the final sample included 400 teeth. Inclusion criteria comprised children demonstrating cooperative behavior (Frankl scores 3–4) and having deep fissures without caries (ICDAS II; DIAGNOdent ≤ 15). Exclusion criteria included systemic disease (ASA $\geq II$), uncooperative behavior, enamel defects, or inability to attend follow-ups. Bitewing radiographs excluded proximal caries. Two calibrated examiners (Cohen's $k \geq 0.8$) conducted the study. Screening of 295 children included health history, caries risk assessment (Cariogram software, Malmö University), and inclusion of those with moderate caries risk. Randomization was two-phased: material pairing (Fuji Triage–GCP Glass Seal / Fuji Triage–Fuji VII EP) was determined using an online randomizer, while tooth allocation (right/left) was assigned by coin toss. Blinding was maintained for participants and evaluators. Before sealant application, baseline data (age, sex, oral hygiene, ICDAS II, and DIAGNOdent scores) were recorded. Teeth were cleaned and isolated; materials were applied per manufacturers' instructions. For Fuji materials, cavity conditioner was used for 10 s, followed by sealant placement, coating, and 20 s LED curing. GCP Glass Seal involved EDTA cleaning, 60 s light-curing, and surface coating with GCP Gloss. All restorations were inspected for marginal adaptation and polymerization, and occlusion was adjusted. Oral hygiene instructions were provided. Follow-up evaluations were conducted at 3, 6, 12, 18, and 24 months by a blinded examiner. Retention, marginal integrity, discoloration, and secondary caries were assessed using modified USPHS criteria. Retention was graded (1 = complete, 2 = partial, 3 = total loss); further caries evaluation (ICDAS II and DIAGNOdent) was performed for scores 2–3.

STATİSTİCAL ANALYSIS PLAN

Data were analyzed using IBM SPSS v21. Descriptive statistics were expressed as mean \pm SD or percentage. Normality was assessed with the Kolmogorov–Smirnov test. Non-parametric tests (Friedman, Kruskal–Wallis with Bonferroni correction) were used where appropriate. Categorical data were analyzed using Fisher-FreemanHalton, Pearson chi-square, or Fisher’s exact tests. Kaplan–Meier curves and log-rank tests compared material survival. Statistical significance was set at $p < 0.05$.

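### One stated size and power (88 teeth per group, 0.80) cannot describe both the within-child and the between-child contrasts, and 88 does not follow from the stated inputs on any standard reading tried

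*Combined protocol and SAP*

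**What the plan says.** The unnumbered protocol text describes 200 children, "each with two fully erupted permanent mandibular first molars (400 teeth), were enrolled". On allocation it states: "Using a split-mouth design, one molar received a high-fluoride glass ionomer-based sealant". The opposite molar gets Fuji VII EP or GCP Glass Seal, and an online randomizer decides which of the two pairings a child receives. No allocation ratio is given.

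The size rests on one calculation, done in G*Power 3.1.9.7 with alpha 0.05 and power 0.80. The assumption about the effect is worded "assuming an effect size of 0.40" and the result is worded "yielding a minimum of 88 teeth per group". The allowance for attrition follows in a separate sentence: "Considering a 15–20% potential loss, the final sample included 400 teeth". The text does not name the test, the effect-size metric, one or two sides, the outcome, the contrast being powered or a within-child correlation.

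The Statistical Analysis Plan section lists Friedman, Kruskal–Wallis with Bonferroni, Fisher-Freeman-Halton, Pearson chi-square, Fisher's exact and log-rank. It does not say whether Friedman compares visits or materials. It names no other method that would respect the pairing of two teeth in one mouth when materials are compared.

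**The concern.** The design contains two kinds of comparison. Fuji Triage against Fuji VII EP and Fuji Triage against GCP Glass Seal are each made inside a mouth, so their precision depends on the number of pairs and on how alike two molars of one child are. The two test materials never share a mouth, so a simple comparison of them is between children and gains nothing from the pairing. At the same number per material, the two kinds have the same power only if the within-child correlation is about 0. A single size in teeth and a single power hide this difference.

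The contrast most exposed is test material against test material. A non-significant result there could be read as if the comparison had 0.80 power, when on the plan's own loss allowance it may have less.

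**Working it through.** **Inputs from the documents.** Effect size 0.40, alpha 0.05, power 0.80, 88 teeth per group, 200 children with two teeth each, loss 15–20%.

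**Assumptions, none of them in the documents.** 0.40 is a standardized mean difference; the test is two-sided unless stated; children split 1:1, giving 200/2 = 100 per pairing; within-child correlation ρ from 0 to 0.7. The t-test is a proxy, because retention is graded 1–3 and the other outcomes are ratings, caries and survival.

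**1. The plan's own figure.** For independent groups, n per group = 2(z₁₋α/₂ + z₀.₈₀)²/d².
- Two-sided: 2(1.960 + 0.842)²/0.40² = 98.1, so 99; the noncentral t gives 100.
- One-sided: 2(1.645 + 0.842)²/0.40² = 77.3, so 78.
- Paired t with dz = 0.40: 52 pairs two-sided, 41 one-sided.
- Mann–Whitney (efficiency 3/π): 105 two-sided, 82 one-sided; at the minimum efficiency of 0.864, 116 and 91.
- Cohen's h = 0.40: 99 two-sided, 78 one-sided.
- ANOVA with f = 0.40: 22 per group for three groups, 19 for four.
- Chi-square with w = 0.40: total 50, 61 and 75 at 1, 2 and 4 df. At 6 and 7 df the totals are 86 and 90, but these are totals, and the df match no comparison described.

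None gives 88 per group. Exactly 88 appears as the total for a 1-df chi-square with w = 0.30, which is not the stated effect size. It is also the smallest group size giving power 0.75, not 0.80, in the two-sided independent t-test.

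**2. Between-child contrast (Fuji VII EP v GCP Glass Seal).** Noncentrality = 0.40·√(n/2), df = 2n − 2.

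| n per group | noncentrality | power |
|---|---|---|
| 88 (stated minimum) | 2.653 | 0.751 |
| 100 (assumed, before loss) | 2.828 | 0.804 |
| 85 (100 less 15%) | 2.608 | 0.737 |
| 80 (100 less 20%) | 2.530 | 0.710 |

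The one-sided power at 88 is 0.84.

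**3. Within-child contrasts (Fuji Triage v each test material).** dz = 0.40/√(2(1 − ρ)), noncentrality = dz·√n, df = n − 1.

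| ρ (assumed) | dz | pairs for 0.80 | power, 88 pairs | power, 80–85 pairs |
|---|---|---|---|---|
| 0 | 0.283 | 101 | 0.747 | 0.705–0.732 |
| 0.2 | 0.316 | 81 | 0.835 | 0.798–0.822 |
| 0.3 | 0.338 | 71 | 0.880 | 0.848–0.869 |
| 0.5 | 0.400 | 52 | 0.960 | 0.942–0.954 |
| 0.7 | 0.516 | 32 | 0.998 | 0.995–0.997 |

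At 88 pairs the power reaches 0.80 near ρ = 0.13. All these figures require a paired analysis.

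**4. Loss.** Keeping 88 after 15–20% loss needs 88/0.85 = 103.5, so 104, up to 88/0.80 = 110 per group. The assumed 100 covers a loss of 1 − 88/100 = 12%.

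**The case against.** The strongest reply is that the documents do not say which calculation was done. A reader might infer from teeth per group, and from the mostly independent-sample tests in the SAP, that the size was worked out for independent groups. The documents do not support this as fact: in a split-mouth trial 88 pairs are also 88 teeth per group, and the independent-groups formula gives 100 or 78, not 88. The basis is unstated, and that is all that can be said.

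A reader might also infer that 0.80 fits none of the three contrasts. That does not hold. The between-child contrast has 0.804 at an assumed 100 per group before loss, and a paired contrast has about 0.80 at 88 pairs with ρ near 0.13. But the first match disappears under the plan's own loss allowance, and the second needs a correlation that the plan never gives.

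Other parts of the reply stand. With positive correlation a properly paired analysis gains power, so the two control contrasts are not harmed by the size. Fuji Triage is labelled the control, and no hypothesis or priority is stated for test against test. The effect-size metric is a guess, so the powers are illustrative for ordinal and survival outcomes. The text is in the past tense, so a recalculation cannot change enrolment; a confidence interval for the test-against-test difference would also guard against over-reading a null result. None of this removes the need to say what the stated power refers to.

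**Conclusion.** The point holds as a statement about the size and power as written. One figure is given for two kinds of contrast that share the same power only if the within-child correlation is near 0, and 88 per group was not reproduced by any standard reading tried.

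If 0.40 is a standardized mean difference and the test is two-sided, the stated 88 gives 0.75 for the between-child contrast, against a stated 0.80. With a 1:1 split, that contrast has 0.71–0.74 after loss. Paired power at 88 pairs spans 0.75 to 0.998 over correlations of 0 to 0.7, conditional on an analysis that the SAP does not specify.

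It would go too far to conclude that the trial as a whole is underpowered: at ρ of about 0.2 or more, a paired analysis of the control contrasts reaches about 0.80 or better even at 80–85 pairs.

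**What to change.** - Restate size and power in children, naming the outcome, test, effect-size metric, sidedness and target contrast, and the split between pairings.
- Correct the 88, or give the inputs that produce it.
- Give two-sample power for Fuji VII EP v GCP Glass Seal after the planned loss, and label it the less powered contrast when the within-child correlation is positive.
- For each control contrast, give matched-pair power over a stated range of within-child correlation.
- Name a paired or clustered between-material analysis in the SAP, so that the matched-pair power applies to the tests actually run.

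The cost is recalculation, an SAP wording change and a less favourable stated power for test against test. No extra children are needed.

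### The minimum of 88 teeth per group cannot be reproduced from effect size 0.40, alpha 0.05 and power 0.80 under any standard test tried

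*Combined protocol and SAP*

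**What the plan says.** The protocol text has one sample-size statement. It names the software ("Sample size was calculated using G*Power 3.1.9.7") and the target ("assuming an effect size of 0.40"), with alpha 0.05 and power 0.80, and reports the result as "yielding a minimum of 88 teeth per group". The enrolled number is then built on that result: "Considering a 15–20% potential loss, the final sample included 400 teeth".

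The design is paired within the child: "Using a split-mouth design, one molar received a high-fluoride glass ionomer-based sealant", and the opposite molar received one of two newer sealants. There are therefore three materials, and every child contributes a control tooth.

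The Statistical Analysis Plan does not refer back to the sample size. It lists rank tests ("Non-parametric tests (Friedman, Kruskal–Wallis with Bonferroni correction) were used where appropriate"), tests for categorical data and a log-rank comparison, with the threshold "Statistical significance was set at $p < 0.05" and no mention of one- or two-sided testing. Neither part of the document says which test, outcome, effect-size metric or number of groups lies behind the 88.

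**The concern.** G*Power returns a definite number once the test and metric are chosen, so a correct statement can be reproduced by trying the plausible choices. Here the usual ones give numbers clearly above or below 88. The missing metric does not explain the gap by itself, because 0.40 read as d, f, w or h fails in each case.

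This is the plan's only justification for its size. If one of the inputs or the result is misreported, readers cannot tell which effect the trial was designed to detect, or with what power.

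**Working it through.** **Inputs.** From the protocol text: effect size 0.40, alpha 0.05, power 0.80, stated result 88 per group. Not stated, so varied here: test, sidedness, metric, pairing, number of groups, allocation ratio.

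**Step 1: attempt to reproduce 88, two equal unpaired groups.** With 0.40 read as Cohen's d, the normal approximation is n per group = 2(z₁₋α/₂ + z₁₋β)²/d².

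- Two-sided, power 0.80: 2(1.960 + 0.842)²/0.16 = 2 × 7.849/0.16 = 98.1, so 99.
- The exact calculation uses the noncentral t distribution with noncentrality d√(n/2) and 2n − 2 degrees of freedom. Power is 0.7997 at 99 and 0.8036 at 100, so 100 per group are needed.
- One-sided, exact: 78 per group.

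**Step 2: other standard readings at 0.40, alpha 0.05, power 0.80.**

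| Reading | Needed |
|---|---|
| Unpaired t, two-sided | 100 per group |
| Unpaired t, one-sided | 78 per group |
| Unpaired t, two-sided, 2:1 allocation | 75 in the smaller group |
| Unpaired t, two-sided, alpha 0.025 or 0.0167 | 121 or 133 per group |
| Rank-sum, normal parent, two-sided or one-sided | 104 or 82 per group |
| Rank-sum, logistic parent, two-sided | 91 per group |
| Rank-sum, minimum A.R.E., one-sided | 91 per group |
| Two proportions, Cohen's h | 99 per group |
| Paired t, two-sided or one-sided | 52 or 41 pairs |
| Three-group ANOVA, f = 0.40 | 22 per group |
| Three-group ANOVA, f = 0.20 | 82 per group |
| Chi-square, w = 0.40, df 1 to 8 | 50 to 94 in total |

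The row f = 0.20 is included because d = 0.40 between two groups corresponds to f = d/2. The chi-square figures are totals, and even as totals they miss 88: df 6 gives 86 and df 7 gives 90. The two rank-sum readings at 91 are the nearest per-group results above 88. Each has power 0.79 at 88 and depends on an option that the document does not mention.

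**Step 3: which change to one input would give 88.** Keep the two-sided, unpaired, equal-group t-test.

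- Change the power: at d = 0.40, power is 0.7465 with 87 per group and 0.7513 with 88. So 88 is the smallest n that reaches 0.75. The normal approximation gives 2(1.960 + 0.674)²/0.16 = 86.8, so 87.
- Change the effect: 88 per group reaches power 0.80 at d of about 0.425.

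**Step 4: power that 88 would give under other readings.**

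- Paired t, 88 pairs, standardised paired difference 0.40: noncentrality 0.40 × √88 = 3.75, power 0.96.
- Unpaired t at 2:1 (176 control, 88 of one new material), d = 0.40: power 0.86.
- One-sided unpaired t, 88 per group: power 0.84.
- Three-group ANOVA, f = 0.20, 88 per group: power 0.83.

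**The case against.** The strongest reply is that the document gives too little for anyone to say what was calculated. The match to power 0.75 needs four unstated choices (two-sided, unpaired, Cohen's d, equal groups) and then overrides an input that is stated. The search is also not exhaustive. A log-rank calculation, or a McNemar-type test for paired binary outcomes, needs event rates or discordance that the document does not give, so neither can be confirmed or excluded. This stands. The 0.75 match is numerical, and the finding is limited to the tests tried.

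A reader might go further and infer that the true planned power is 0.75, with a 25% rather than 20% chance of missing the target effect, or that the trial is underpowered. The document does not support either. The 25% holds only for the one reading in Step 3, and the plan never says that this is the comparison it powered. Under the readings in Step 4, including the within-child comparison that the split-mouth design suggests, 88 is more than enough.

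A reader might also note that 400 teeth would leave about 100 per new material if children were split equally between the pairings (an assumption). A 15–20% loss would then leave 80–85 per group, with unpaired two-sided power of 0.71–0.74 at d = 0.40. That describes a comparison of the two new materials between children, which is not named as the basis of the sample size.

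The reply does not make 88 follow from 0.40, 0.05 and 0.80. Under-specification explains why the error cannot be located, but it does not remove the inconsistency.

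**Conclusion.** The point holds as a failure to reproduce. Under every standard test tried, the stated inputs give a per-group figure other than 88, from 22 (three-group ANOVA, f = 0.40) to 104 (two-sided rank-sum, normal parent) at unadjusted alpha and the main settings. The nearest per-group results are 82 below and 91 above.

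Confidence is high that the reported figure and its stated basis do not fit together under these tests. It is low on which element is wrong. If the basis was a two-sided, unpaired, equal-group comparison with Cohen's d, the discrepancy is 12 teeth per group (100 − 88, or 14% of 88), equivalently 0.05 in power or about 0.025 in d. On a paired basis, 88 exceeds the 52 pairs needed. No conclusion about the trial's actual power follows.

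**What to change.** State the test, sidedness, effect-size metric, pairing, number of groups and allocation ratio used in G*Power. Then re-run the calculation and correct whichever figure is wrong. The replacement depends on what was done:

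- If the basis was a two-sided unpaired comparison of two equal groups with Cohen's d, report one of three consistent statements: 100 per group for power 0.80, power 0.75 at 88 per group, or a detectable d of about 0.425 at power 0.80.
- If the basis was the within-child split-mouth comparison, report the paired calculation instead, with the standardised paired difference or the discordance assumed.
- If it was another test, such as log-rank, give the extra inputs that it needs.

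None of these figures should be adopted just because it fits; it should reflect the calculation actually made. The cost is wording only. Enrolment is unchanged and no extra children are needed, although a stated figure may become slightly less favourable.

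### The 15–20% loss allowance does not preserve the plan's minimum of 88 teeth in both test-material groups: 160–170 test teeth remain, and 176 are needed

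*Combined protocol and SAP*

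**What the plan says.** The design and sample size are in the unnumbered protocol text of the combined document.

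- Enrolment: "A total of 200 healthy children (ASA I), aged 6–12 years, each with two fully erupted permanent mandibular first molars (400 teeth), were enrolled".
- Control tooth: "Using a split-mouth design, one molar received a high-fluoride glass ionomer-based sealant".
- Test tooth: "the contralateral molar was treated with either a CPP-ACP-containing sealant (Fuji VII EP, GC Corp.) or a nano-fluorohydroxyapatite-based sealant".
- Allocation: "material pairing (Fuji Triage–GCP Glass Seal / Fuji Triage–Fuji VII EP) was determined using an online randomizer". The ratio is not given.
- Sample size: an effect size of 0.40, alpha 0.05 and power 0.80, "yielding a minimum of 88 teeth per group".
- Loss: "Considering a 15–20% potential loss, the final sample included 400 teeth".

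The section headed Statistical Analysis Plan adds that "Kaplan–Meier curves and log-rank tests compared material survival". The documents do not define the word group in the sample size statement. They also do not name the test, its sidedness or the type of effect size behind the 88.

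**The concern.** The loss sentence tells the reader that the sample was sized so that 15–20% attrition could be absorbed. The total of 400 teeth looks generous against 88 per group, but the total is not what matters. Half of the teeth belong to the control material by design, and two test materials divide the other half. The margin therefore has to be checked for each test material.

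If the margin is too small, a reader who sees 15% loss over the 24 months of follow-up would wrongly conclude that the plan's minimum had been met for every material. The groups affected are the two new sealants that the trial sets out to evaluate.

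**Working it through.** **Inputs, all from the protocol text.** 200 children with one control tooth and one test tooth each; two test materials; a minimum of 88 per group; loss of 15–20%. I take group to mean material, because the analysis plan compares materials. I take loss to occur by child, because a child who leaves a split-mouth trial takes both teeth.

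**Step 1. Can the plan's own figures be reproduced?** Not from what is stated.

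- *The 88.* With effect size 0.40, alpha 0.05 and power 0.80, a two-sample t test needs 100 per group two-sided or 78 one-sided. A paired t test needs 52 pairs two-sided. A three-group ANOVA with f = 0.40 needs 64 in total. A chi-square test with w = 0.40 needs 86 in total at 6 degrees of freedom and 90 at 7. None gives 88 per group. As the test is not named, this does not show that 88 is wrong, and the steps below take 88 as given.
- *The 400.* Holding 88 after loss needs 88/0.85, rounded up to 104, or 88/0.80 = 110 per group:

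| Equal groups | 15% loss | 20% loss |
|---|---|---|
| 2 | 208 | 220 |
| 3 | 312 | 330 |
| 4 (pairing by material) | 416 | 440 |

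None of these ranges contains 400. Two or three equal groups would need fewer than 400, but the design does not have three equal groups: the control takes half the teeth.

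**Step 2. Test teeth left after loss.**

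- 15% loss: 200 × 0.85 = 170
- 20% loss: 200 × 0.80 = 160
- Needed for both test materials: 2 × 88 = 176
- Shortfall: 176 − 170 = 6, up to 176 − 160 = 16

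Both remaining totals are below 176, so no split can leave 88 in each test group. This step needs neither the allocation ratio nor equal loss in the two pairings, only the overall loss by child.

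**Step 3. Per test material.** The 1:1 split is an assumption. An uneven example is added, and equal loss in both pairings is assumed.

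| Starting size | After 15% | After 20% | Largest loss that keeps 88 |
|---|---|---|---|
| 100 (1:1) | 85 | 80 | 1 − 88/100 = 12% |
| 95 (smaller group of an uneven split) | 80.75 | 76 | 1 − 88/95 = 7.4% |

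At 1:1 the shortfall is 88 − 85 = 3 to 88 − 80 = 8 teeth per test material.

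**Step 4. Control.** 200 × 0.85 = 170 and 200 × 0.80 = 160, both well above 88.

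**Step 5. Rough effect on power.** This is illustrative only, because the effect-size type and test are assumptions. For a two-sided two-sample t test with d = 0.40, treating teeth as independent:

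| Comparison | Power |
|---|---|
| 88 v 88 | 75.1% |
| 85 v 85 | 73.7% |
| 80 v 80 | 71.0% |
| 85 test v 170 control | 85.1% |
| 80 test v 160 control | 82.9% |

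If the effect is instead set so that 88 v 88 gives exactly 80%, then 85 v 85 gives 78.6% and 80 v 80 gives 76.1%.

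**The case against.** The subtraction is not in dispute. The case against giving it weight has five parts.

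- **Inflation convention.** Some planners add the percentage on instead of dividing by one minus the loss. Then 88 × 1.15 = 101.2 and 88 × 1.20 = 105.6 are needed per group. The 100 available at 1:1 is an uplift of 100/88 − 1 = 13.6%. The gap shrinks to about one tooth per group at 15% and 5 to 6 at 20%, but it does not close.
- **Meaning of group.** If all test teeth were pooled against control, 160–170 would far exceed 88. That reading merges two different products and does not fit a plan that compares materials. Counting four pairing-by-material groups of 100 gives the same shortfall as counting by material at 1:1.
- **Control surplus.** This stands. If each test material is compared with all control teeth, power after loss can exceed that of 88 v 88, as Step 5 shows. The loss of 1 to 4 points applies only to test-versus-test or other equal-sized comparisons. The plan does not say which contrast was powered.
- **Censoring.** This also stands. In the Kaplan–Meier and log-rank analysis, children lost early normally contribute up to their last visit. The counts of 80–85 describe complete 24-month data.
- **Origin of 88.** The unspecified calculation behind 88 is arguably the more basic gap, and rerunning it depends on recovering its inputs. That supports naming those inputs and leaves the mismatch in place.

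**Conclusion.** The concern holds. At the loss the plan itself allows for, 160–170 test teeth remain where 176 are needed, so at least one test material ends below the stated minimum at any allocation ratio. At 1:1 the shortfall is 3 to 8 teeth per test material, and the true tolerance is 12% at best.

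The conclusion rests on reading group as material and on loss by child. The per-material figures also assume a 1:1 split and equal loss in both pairings. The conclusion does not depend on how 88 was obtained.

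The size is modest. The control group is not short, and nothing here shows that the trial as a whole is underpowered. The loss allowance is wrong as written and should be corrected.

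**What to change.** Do not enrol more children. Make three changes to the sample size text:

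1. Replace the loss sentence with one to this effect: 200 children give about 100 pairs per test material if allocated 1:1; at 15–20% loss 80–85 pairs per test material have complete 24-month data; the minimum of 88 per test material is kept only if loss is at most 12%.
2. State the allocation ratio and the number of children allocated to each pairing, and say what group means.
3. Report power at 80–85 per test material using the calculation that produced 88. Name its test, sidedness, effect-size type and the contrast it refers to. If those inputs cannot be recovered, say so.

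The cost is a restated sentence, a few reported details and one rerun of the existing G*Power calculation. Enrolment and conduct do not change. The stated margin becomes slightly less favourable.

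### Baseline child and tooth measures are recorded, but no planned test adjusts for them or for the child; the comparison of the two newer sealants stays valid but may forgo some precision

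*Combined protocol and SAP*

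**What the plan says.** The unnumbered protocol text reports that "baseline data (age, sex, oral hygiene, ICDAS II, and DIAGNOdent scores) were recorded" before sealant application. Age, sex and oral hygiene belong to the child; ICDAS II and DIAGNOdent belong to the tooth. The documents do not say what these values are for in the analysis.

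The Statistical Analysis Plan names three groups of methods:

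- Non-parametric: "Non-parametric tests (Friedman, Kruskal–Wallis with Bonferroni correction) were used where appropriate".
- Categorical: "Categorical data were analyzed using Fisher-FreemanHalton, Pearson chi-square" or Fisher's exact tests.
- Survival: "Kaplan–Meier curves and log-rank tests compared material survival".

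No regression, Cox, GEE or mixed model is named, and no stratified log-rank. Friedman blocks on a unit but takes no covariate.

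The protocol text describes two randomisation steps. The material pairing is drawn per child; the side of the mouth is then set by coin toss. Every child has one Fuji Triage tooth and one tooth with either Fuji VII EP or GCP Glass Seal. No stratification of the pairing is described.

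**The concern.** Fuji VII EP v GCP Glass Seal is a comparison between two sets of children. Enrolment runs from 6 to 12 years, and oral hygiene is not an eligibility criterion. Differences between children in these respects therefore add noise to the comparison. If they predict retention or survival, a model that uses them would estimate the material difference more precisely from data already in hand.

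The same noise remains in the comparisons with Fuji Triage. The split-mouth design would remove it, but only under a paired or child-level analysis, and the listed between-material tests treat the teeth as independent.

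What is at stake is power and the width of the intervals, most plainly if follow-up losses reach the upper end of the planned allowance.

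**Working it through.** **The plan's own figure.** The sample size was found by "assuming an effect size of 0.40, $\alpha = 0.05$, and power = 0.80", "yielding a minimum of 88 teeth per group". The type of effect size, the test and its sidedness are not stated. Read as a standardised mean difference d = 0.40, a two-sample t-test needs 100 per group two-sided or 78 one-sided, so 88 is not reproduced. At 88 per group the two-sided power is about 0.75. This is a separate matter and does not decide the present point; d = 0.40 is used below as an assumption.

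**Inputs.**

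- Children: 200 (protocol text), taken as 100 per pairing. The ratio is not stated; 1:1 is assumed.
- Loss: "Considering a 15–20% potential loss, the final sample included 400 teeth". At the upper end, 100 × (1 − 0.20) = 80 per group.
- Level: "Statistical significance was set at $p < 0.05", taken as two-sided.
- R², the share of outcome variance explained by the covariates: not in the documents, so a range is used.

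**Between-child comparison, normal-outcome approximation.** Adjustment shrinks the residual SD by √(1 − R²), so the effective effect size is d/√(1 − R²). Power comes from the noncentral t with 158 df and noncentrality [d/√(1 − R²)] × √(80/2).

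| R² | Effective d | Noncentrality | Power |
|---|---|---|---|
| 0 | 0.400 | 2.53 | 0.710 |
| 0.02 | 0.404 | 2.56 | 0.719 |
| 0.05 | 0.410 | 2.60 | 0.732 |
| 0.10 | 0.422 | 2.67 | 0.755 |
| 0.25 | 0.462 | 2.92 | 0.827 |

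The gain is 1–2 points at R² 0.02–0.05, 4 to 5 points at 0.10 and about 12 at 0.25.

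**The child's own Fuji Triage tooth.** In a mixed model this tooth also informs the comparison of the two newer materials. If outcomes of the two teeth correlate at r, it alone gives R² of about r²: 0.09 at r = 0.3 (power 0.75) and 0.25 at r = 0.5 (power 0.83). Both correlations are assumed.

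**Categorical outcomes.** The formula above is for a continuous outcome, whereas retention is a three-level grade and the other ratings are categorical. A simulation (100 per arm, 3,000 runs, conditional log-odds ratio 0.8, one covariate, error about 0.7 points) compared chi-square with adjusted logistic regression:

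| Covariate log-odds per SD | Chi-square | Adjusted |
|---|---|---|
| 0 | 81.5% | 80.0% |
| 0.3 | 80.9% | 80.4% |
| 0.6 | 76.6% | 77.8% |
| 1.0 | 68.1% | 73.7% |

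A clear gain appears only with a strong covariate. A second simulation at 80 per arm, with two covariates of which one is prognostic and a likelihood-ratio test, matched chi-square within simulation error when that covariate was weak. At log-odds 0.6–1.0 it gained about 4–8 points with a 40% event rate and 2–5 points with a 5% rate.

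**Where else precision may be lost.** For a comparison with Fuji Triage with 100 pairs and d = 0.40 (normal approximation), power under a paired analysis is 80.7% at within-child correlation 0, 84.6% at 0.1, 92.2% at 0.3 and 97.9% at 0.5. Ignoring the child could therefore cost at least as much there.

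**The case against.** **The gain is not demonstrated.** The documents give no link between any baseline variable and outcome. Eligibility admits only caries-free fissures with DIAGNOdent of 15 or less, in children at moderate caries risk. ICDAS II must then be nearly constant, and DIAGNOdent has little range. This stands. It is why the low R² rows matter as much as the high ones, and why age and oral hygiene are the better candidates.

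**Adjustment can cost power.** With five covariates, one of them prognostic, 80 per arm and a 5% event rate, a simulation (1,500 runs, assumed rates) gave chi-square v adjusted 56.5% v 50.9% when that covariate had no effect and 56.2% v 60.3% when it was strong (log-odds 1.0). Up to 3% of fits were not estimable. This stands against a long covariate list for rare events such as secondary caries might be. The two-covariate result shows that it does not rule out a short list.

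**Stronger readings that the documents do not support.** A reader might infer that missing adjustment biases the results or inflates type I error through chance imbalance. It does not: the pairing is randomised. A reader might also place the loss mainly in Fuji VII EP v GCP Glass Seal. That would need paired analysis of the other contrasts, which is not what is listed, and the documents name no primary contrast. Finally, 1/(1 − R²) gives 1.11 at R² = 0.10 and 1.33 at 0.25, which could be read as 11–33% more teeth for free. That holds only for a normal outcome at those assumed R² values.

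**Conclusion.** The point holds as an efficiency recommendation. No covariate-adjusted or child-level model is planned, although the baseline data exist and one of the material comparisons is between children. The possible gain in that comparison runs from about 1 point of power (R² 0.02) to about 12 (R² 0.25), starting from 0.71. This rests on assumed d = 0.40, 1:1 pairing, 20% loss, a two-sided test and a normal outcome. For the categorical outcomes the gain may be near nil, or slightly negative, unless a covariate is strongly prognostic.

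**What to change.** For retention and survival, name a model with a child effect or child-clustered errors: an ordinal or logistic mixed model or GEE for retention, and a Cox or discrete-time model for survival. Include material, age and oral hygiene. Baseline DIAGNOdent is optional; leave out ICDAS II, which eligibility makes nearly constant. For secondary caries, use fewer covariates or none if events are few. Keep the listed unadjusted tests as supportive.

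The plan is written in the past tense. If outcomes have already been seen, label the adjusted analysis post hoc.

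The cost is wording in the Statistical Analysis Plan and modest analysis work, with no new data. The downside is a possible small loss of power if the covariates turn out not to be prognostic.
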